10.5. Demographic and Baseline Characteristics

Demographics (age, sex, race, and ethnicity) as well as height (cm), weight (kg), and BMI at baseline will be summarized for the safety population using descriptive statistics. All demographic data will be provided in a data listing.

IgAN disease duration, calculated from time of first renal biopsy diagnosis to Study Day 1, will be summarized with descriptive statistics.

10.6. Titration and Run-In Periods

The following data collected during the titration (if applicable) and run-in periods will be listed by subject and summarized:

- Blood pressure measurements (supine, after at least 3 minutes of rest);
- RAAS blocker(s) type and dose titration detail;
- Serum creatinine and eGFR measurements;
- Urinary PCR and ACR measurements;
- Urinary MCP-1:creatinine ratio, EGF:MCP-1 ratio, and urinary microscopic RBC count data;
- Changes in concomitant medications, with particular attention to the dose(s) of RAAS blocker(s), and
- Any pre-treatment adverse events reported.

10.7. Efficacy Evaluation

10.7.1. Change in slope of first morning urinary PCR (protein:creatinine ratio) from the 8-week RAAS blocker run-in period to the 12-week treatment period

Slope will be calculated for each subject using the time points as follows.

Time Window for Slope Calculation	Time Points Used for Slope Calculation	Corresponding Time Value Used for Regression*
Weeks -8 to -5	Day -63 and Day -35	-63 and -35
Weeks -4 to -1	Day -35, Day -7 to 02, and Day 1	-35, -5, and 0
Weeks -8 to -1	Day -63, Day -35, Day -7 to 02, and Day 1	-63, -35, -5, and 0
Weeks 1 to 4	Day 1, Day 8, Day 15, and Day 29	0, 7, 14, 28
Weeks 1 to 12	Day 1, Day 8, Day 15, Day 29, Day 57, and Day 85	0, 7, 14, 28, 56, and 85

* For Time Point Day -7 to -2, time value of -5 will be used. For Study Day on/after the first dose, one day is subtracted to return the value to continuous scale such that Day 0 is day of first dose.

For the primary efficacy endpoint analysis, the slope of the urinary PCR during the 8-week run-in period, during the initial 4-week treatment period, as well as the full 12-week treatment period will be calculated for each subject. The mean slope for the 8-week run-in period will be compared to the mean slope for the initial 4-week, as well as the full 12-week treatment period to evaluate the treatment effect of CCX168.

If the slope for the first 4 weeks of the run-in period is steeper than the slope of the last 4 weeks of the run-in period, indicating that steady state has not been achieved over the first 4 weeks, the slope of the last 4 weeks of the run-in period will be used as the baseline slope, instead of the slope over the 8 weeks of the run-in period. This comparison will be performed by the paired t-test. The 95% confidence interval for the difference in the mean slopes will be presented.

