After the 8-week run-in period has been completed, two back-to-back first morning urine collections need to be obtained for protein and creatinine measurements. The geometric mean of the two urinary PCR measurements must be > 1 g/g creatinine for eligibility for further study participation.

On Day 1, patients meeting inclusion criteria will start CCX168 treatment. Patients will take CCX168 30 mg orally twice daily for 12 weeks (84 days). The CCX168 dose will be taken in the morning optimally within one hour after breakfast and in the evening optimally within one hour after dinner. After the 84-day treatment period, patients will be followed for 12 weeks (84 days) while continuing to take their RAAS blocker treatment at a stable dose.

At post-Day 1 study visits, blood and urine samples will be collected for safety, efficacy, and pharmacokinetic measurements. A serum pregnancy test for women of childbearing potential will be done on Days 29, 43, 57, 85, 113, and 169. Physical examinations and vital signs assessments will be performed throughout the study. Concomitant medication and adverse event assessments will be made at every study visit. An optional renal biopsy could be performed after the 12-week treatment period to assess the effect of CCX168 treatment on kidney histology.

During the 12-week treatment period and the 12-week follow-up period, the dose(s) of RAAS blocker(s) must remain unchanged. No new RAAS blocker or non-dihydropyridine calcium channel blocker or diuretic may be added during the study period (active treatment period or follow up).

During the treatment period with study medication and the 12 weeks of follow up thereafter, no new immunomodulatory medication may be started including, but not limited to cyclosporine, tacrolimus, mycophenolate mofetil, azathioprine, cyclophosphamide, or glucocorticoids (e.g. prednisone).

Concomitant use of omega-3 fatty acid supplements (e.g., fish oil) is permitted IF the medication is started at the time of, or before screening, and is maintained at a stable dose during the rest of the study until the end of the follow-up period (Day 169).

Patients will visit the study center on Days 1, 8, 15, 29, 43, 57, 85, 113, 141, and 169 for the treatment and follow-up period.

Duration of treatment with study medicine: 84 days

Duration of follow up after end of treatment with study medicine: 84 days

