6.3.3. Study Day -7 to -2 Window

Two back-to-back study visits will occur within the Study Day -7 to -2 window, relative to Study Day -63. The following procedures will be performed on these two study days:

- Blood pressure in the supine position after at least 3 minutes of rest (on both days);
- Serum pregnancy test for women of child-bearing potential (on the first of the two days);

- Serum creatinine for an eGFR calculation (on the first of the two days);
- First morning urinary protein and creatinine measurements for a PCR calculation (on both days);
- First morning urinary albumin, MCP-1, EGF, and microscopic RBC count for ACR, MCP-1:creatinine, EGF:MCP-1 ratio, and hematuria assessment (on the first of the two days);
- Recording of changes in concomitant medication;
- Recording of all adverse events;
- If the subject is still eligible for study continuation, i.e.:
 - If the geometric mean of the two first morning urinary PCR levels is still $> 1 \text{ g/g}$ creatinine but $\leq 8 \text{ g/g}$ creatinine,
 - If the subject's eGFR has not deteriorated $> 10 \text{ mL/min/1.73 m}^2$ over the prior 8-week run-in period,

the subject will come for their Study Day 1 visit. The subjects will be reminded to stay on a stable dose(s) or their RAAS blocker(s). If a subject is not eligible at this stage, the subject will be discontinued from study.

6.4. Study Day 1

If eligible for continuation in the study, the subject will visit the study center on Day 1 for the following procedures:

- A physical examination (excluding genitourinary, ophthalmic, and female breast assessments); body weight assessment will be performed;
- Vital signs (temperature, blood pressure, heart rate) will be measured supine after at least 3 minutes of rest;
- Serum chemistry and hematology; an eGFR will be calculated based on MDRD equation;
- Urinalysis, including pH, specific gravity, glucose, nitrite, ketones, bilirubin, urobilinogen, RBCs, and WBCs on a first morning urine sample collection;
- Urinary protein, creatinine, albumin, MCP-1, EGF, and microscopic RBC count on a first morning urine sample collection;
- Serum IgA and plasma C3 measurement;
- A plasma sample will be collected for baseline PD marker and PK measurement;
- A urine sample will be collected for PD marker assessment;
- Any changes in concomitant medication use will be recorded;

Note that the above listed procedures must be performed prior to taking study medication.

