7.10.4. Efficacy Analyses

The primary efficacy endpoint is the change in slope of first morning urinary PCR from the 8-week RAAS blocker run-in period to the 12-week CCX168 treatment period.

For the primary efficacy endpoint analysis, the slope of the urinary PCR during the 8-week run-in period, during the initial 4-week, as well as the full 12-week treatment period will be calculated for each subject. The mean slope for the 8-week run-in period will be compared to the mean slope for the initial 4-week, as well as the full 12-week treatment period to evaluate the

treatment effect of CCX168. If the slope for the first 4 weeks of the run-in period is steeper than the slope of the last 4 weeks of the run-in period, indicating that steady state has not been achieved over the first 4 weeks, the slope of the last 4 weeks of the run-in period may be used as the baseline slope, instead of the slope over the 8 weeks of the run-in period. This comparison will be performed by the random coefficients regression model with the test for slope-by-period (pre and on-treatment) interaction.

Similar analyses will be performed for the urinary ACR, eGFR, urinary MCP-1:creatinine ratio, urinary EGF:MCP-1 ratio, and urinary microscopic RBC count.

The proportion of subjects achieving renal response, defined as an improvement in urinary PCR based on a decrease from baseline to each subsequent time point in urinary PCR to a level < 300 mg/g creatinine and maintaining estimated glomerular filtration rate (eGFR) within 15% of baseline, will be calculated and summarized.

The same summary will be provided for subjects achieving partial renal response, i.e., a urinary PCR reduction to a level < 1 g/g creatinine while maintaining an eGFR within 15% of baseline.

Summary statistics at each time point will be calculated for each of the efficacy endpoints. For categorical endpoints, numbers and percentages will be calculated. For continuous variables, numbers, means, medians, ranges, and standard deviations will be calculated. Geometric means will be calculated at each time point for urinary PCR, ACR, and MCP-1:creatinine, and other measurements that are not normally distributed.

The 84-day follow-up period results for the endpoints listed above will also be summarized.

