10.2.4. Definition of Baseline

For all analyses, baseline will be defined as the most recent measurement prior to the date and time of the first administration of CCX168. Baseline can be on the same day as the first dose of study medication, but prior to administration of study drug (typically the Day 1 pre-dose value). For urinary PCR, baseline will be the geometric mean (GM) of the two measurements made in the Day -7 to -2 window plus the Day 1 (pre-dose) value. For the eGFR, urinary ACR, MCP-1:creatinine ratio, EGF:MCP-1 ratio, and microscopic RBC count, baseline will be the geometric mean of the one measurement made in the Day -7 to -2 window plus the Day 1 (pre-dose) value.

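### The two PCR samples that decide entry at the end of run-in are reused in the run-in slope and in the PCR baseline, so both PCR results can lean modestly toward benefit when many subjects lie near 1 g/g

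*SAP*

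**What the plan says.** **Entry.** Protocol 3 states: "The geometric mean of the two urinary PCR measurements must be > 1 g/g creatinine for eligibility for further study participation". Protocol 6.3.3 repeats the check ("If the geometric mean of the two first morning urinary PCR levels is still" above 1 g/g) and adds an upper limit of 8 g/g. On failure: "If a subject is not eligible at this stage, the subject will be discontinued from study". Such a subject is never dosed, and every population in SAP 8 requires a dose.

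**Primary endpoint.** SAP 10.7.1 builds the run-in slope from "Day -63, Day -35, Day -7 to 02, and Day 1". The table footnote shows that the third entry means Day -7 to -2: "For Time Point Day -7 to -2, time value of -5 will be used". The treatment slope uses "Day 1, Day 8, Day 15, Day 29, Day 57, and Day 85". The two slopes are compared by paired t-test. Protocol 7.10.4 had named a "random coefficients regression model with the test for slope-by-period" interaction.

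**Baseline.** SAP 10.2.4 says that for PCR the "baseline will be the geometric mean (GM) of the two measurements made in the Day -7 to -2 window", taken together with the Day 1 pre-dose value. SAP 10.7.5 bases percent change on the ratio of visit to this baseline.

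**Not stated.** SAP 10.7.1 does not say whether PCR is logged before slopes are fitted, or whether the two samples enter as two points or as one average. SAP 5.1 describes a single-arm study. No planned analysis omits the two samples or corrects for their role in selection.

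**The concern.** A subject whose underlying PCR is close to 1 g/g passes more easily when the two deciding samples happen to read high. Among those who go on, the sampling error in these two values is therefore positive on average. Using the same values again as data carries that error into the results in two separate ways:

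- In the run-in slope they are late points, so high values make PCR appear to rise, or to fall less, before treatment. The treatment slope does not use them. Treatment minus run-in then moves in the negative direction, which reads as benefit.
- In the baseline they hold two thirds of the weight, so later visits look improved by comparison.

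With no control arm, the run-in slope is the only reference for the primary endpoint. Subjects near the threshold are plausible. The protocol rationale aims at a relatively modest degree of proteinuria, and some subjects start or increase RAAS blockade between screening and this check.

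**Working it through.** **1. The plan's own figure.** The documents give no figure for this effect. Their only slope figures are in SAP 10.1: difference 4.6, about 80% power with 15 subjects and 90% with 20.
- SD of the difference √2 × 4.77 = 6.75, two-sided 0.05: 69.0% and 82.4%.
- Same SD, one-sided 0.05: 80.7% and 90.2%, which matches, but this variant is not stated.
- 1.32 with SD 1.67, two-sided 0.05: 81.2% and 91.8%, which matches, but the difference is not 4.6.

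These are ACR slopes in vasculitis. They give no sampling SD for PCR in IgAN and are not used below.

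**2. Weight of the two samples in the run-in slope.** The least-squares weight of a point is (t − mean t) / Σ(t − mean t)².
- One averaged point: times -63, -35, -5, 0; mean -25.75; sum of squares 2566.75. Weights per day: -0.0145, -0.0036, +0.0081, +0.0100.
- Two separate points: times -63, -35, -5, -5, 0; mean -21.6; sum of squares 2911.2. Each sample has 16.6 / 2911.2 = +0.0057, together +0.0114.

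The weight is positive either way.

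**3. From selection to bias (log PCR, independent errors).** Let δ be the mean log error of the two samples among those who pass. The run-in slope shifts by 0.0114δ or 0.0081δ per day, and log percent change by -(2/3)δ. An assumed central case (median 1.5 g/g, between-subject log SD 0.5, within-subject log SD 0.3, 20% fall by run-in, 78% pass) gave a Day 85 change of -2.7% with an inert drug, so δ = 1.5 × 0.0274 = 0.041. With two points:
- Tilt: 0.041 × 0.0114 = 0.00047 per day. Over 84 days that is 0.039 on the log scale, a false fall of about 3.9%.
- SD of the contrast: 0.3 × 0.0248 = 0.00745 (the factor 0.0248 is derived in step 5).
- Standardised bias: 0.00047 / 0.00745 = 0.063. At n = 20 the noncentrality is 0.063 × √20 = 0.28, and the chance of a significant false benefit about 4.5%.

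With one averaged point the same steps give 2.7% and about 3.8%.

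**4. Simulations of an inert drug.** n = 20, two-sided 5% paired t-test, 12-week contrast. All PCR distributions are assumed. The nominal rate in the benefit direction is 2.5%; with no entry check it was 2.4% to 2.7%.

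| Assumptions | Samples in slope | Samples left out |
|---|---|---|
| Log PCR, two points, median 1.3–2.0 g/g, 20% fall by run-in | 3.3–6.1% | |
| Central case, across scales and entry rules | 3.2–4.7% | 1.9–2.6% (independent-error runs) |
| Median 2 g/g, 95–97% pass | 2.4–3.1% | |
| Median 3 g/g, log PCR | 2.4–2.5% | |
| Extreme: median 1.2 g/g, within-subject log SD 0.5, about half fail | 6.3–12.6% | |
| Raw PCR, two samples collapsed to geometric mean | 1.7–3.1% | |
| Serial correlation, 7-day value 0.3–0.6, raw PCR | 5.3–5.8% | 3.8–5.0% |
| Serial correlation, 7-day value 0.4, log PCR | 11.2% | 7.0% |

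Errors are independent except in the last two rows. Correlation matters because Day 1 then shares the positive error, and Day 1 both ends the run-in slope and starts the treatment slope.

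The Day 85 percent change with an inert drug was -0.3% to -13% over the whole independent-error range, and about -0.7% to -6% at medians of 1.3–2.0 g/g with the 20% fall. Against Day 1 alone it was about 0% with independent errors, and -3.6% to -5.5% with the 7-day correlations of 0.3–0.6.

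**5. Price of leaving the samples out.** With independent errors, the contrast variance per unit error variance is the squared run-in weights other than Day 1, plus the squared difference of the two Day 1 weights, plus the remaining squared treatment weights.
- Two points kept: 0.000288 + 0.000177 + 0.000151 = 0.000617 after rounding; SD 0.0248.
- Samples left out (times -63, -35, 0): 0.000233 + 0.000497 + 0.000151 = 0.000881; SD 0.0297.

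The ratio is 1.195, so the SD is about 20% larger.

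**The case against.** The strongest reply is that neither direction nor size is fixed by the written plan. Much of this stands.

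- **Scale and entry rule.** The SAP speaks of the slope of urinary PCR without a transformation. On raw PCR with the two samples collapsed to their geometric mean, which is the statistic that decides entry, averaging pulls that point down. With independent errors this offsets or slightly reverses the net lean. A reader might infer that the plan favours the drug whatever the details; the documents do not support that.
- **Upper limit.** The 8 g/g limit selects the other way, and at a typical PCR of about 3 g/g the lean vanishes on log PCR. A true continuing fall under RAAS blockade during run-in would also push against benefit.
- **Baseline.** A reader might infer that the two-thirds share of the baseline drives the primary result. It does not. The primary contrast compares two slopes; the baseline feeds percent change, shift and response summaries.
- **Remedy.** A reader might infer that dropping the two samples removes the bias. That needs errors that are independent between visits; with serial correlation part of the bias stays.
- **Proportion.** The protocol rationale cites an ACR fall of about 60% in vasculitis, so a shift of a few percent could not by itself explain an effect of that order. The rule in SAP 10.7.1 that swaps in the last-4-week slope is a separate and larger matter: read as applying to each subject, it gave about 31% false benefit without the entry check and 33% with it.

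What the reply does not remove is the selection and reuse themselves, in a study with no other control and no planned check. Listing and summarizing the run-in PCR values (SAP 10.6) shows the data but does not correct the contrast.

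**Conclusion.** The reuse is certain from the documents; its consequence is conditional. When many subjects lie near 1 g/g, the run-in slope is tilted up and the primary contrast leans modestly toward benefit. With independent errors and plausible distributions, the false-benefit rate is roughly 2.5% to 6% against 2.5% nominal. Serial correlation raises it, as does a population in which about half fail the check. It is near zero at about 3 g/g, and cancelled or slightly reversed on raw PCR with the two samples collapsed to their geometric mean. The percent change in PCR is flattered separately, by about 2.7% in the central case. Every size rests on assumed medians, SDs and correlations, because the documents supply none. This justifies a prespecified sensitivity analysis. It does not invalidate the primary analysis or call for a change to the entry rule.

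**What to change.** - **SAP 10.7.1:** add a prespecified sensitivity paired t-test whose run-in slope uses Days -63, -35 and 1 only.
- **SAP 10.7.5:** also report percent change in PCR against the Day 1 pre-dose value alone.
- **For both:** state that they reduce the selection effect, and remove it only if errors are independent between visits.
- **Optional:** fit the random-coefficients model of Protocol 7.10.4 to everyone who entered run-in, including those stopped at the end-of-run-in check, whose run-in PCR values are already collected. This needs a newly defined analysis set, since every current SAP population requires a dose, and a stated error structure.

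**Cost:** a little extra analysis and SAP wording, with no new visits or samples. The sensitivity contrast has an SD about 20% larger, so it will be less precise than the primary test. The optional model takes more work to specify.

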4.4. Removal of Subjects from Therapy or Assessment

Subjects may be terminated early from the study for any of the following reasons:

1. Subject request: Subjects may withdraw their consent to participate in the study at any time without prejudice.
2. Investigator request: The Investigator may withdraw a subject if, in his/her clinical judgment, it is in the best interest of the subject or if the subject cannot comply with the protocol.
3. Sponsor request.

In the event of withdrawal from the study prior to the Day 85 visit, the tests and evaluations listed for Study Day 85 should be carried out as part of the Early Termination visit, whenever possible. For subjects who withdraw after Day 85, the Day 169 study procedures should be performed. The Sponsor should be notified of all study withdrawals in a timely manner.

Subjects who experience a decrease from baseline in eGFR $>$ 10 mL/min/1.73 m² or $>$ 20%, (confirmed by repeat after 2 weeks) which is otherwise not explained (e.g., dehydration, new medication), or an increase in proteinuria of $>$ 3 g/g creatinine from baseline or to a level $>$ 8 g/g (confirmed by repeat after 2 weeks) during the 12-week treatment period, will exit the treatment phase of the study and be treated at the discretion of their primary nephrologist. They will remain in the study for follow up and outcome recording.

In the event of treatment failure where rescue treatment such as corticosteroid therapy is needed, the study drug (CCX168) will be discontinued, and appropriate SOC measures will be taken. However, the subject will be asked to remain in the study and complete all remaining study visits. If this is not possible, an attempt will be made to complete all procedures scheduled for the Day 85 visit (if the rescue event occurred prior to the Day 85 visit) and Day 169 (if the rescue event occurred after the Day 85 visit).

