6. DEFINITIONS

Table 1. Terminology and Definition

Terminology	Definition
Age	Age is calculated as the number of full years since date of birth at the time of signing the Informed Consent Form (ICF).
Study Drug	CCX168
Study Day	The number of days relative to the very first day when the subject receives a dose of the study drug. For visits prior to the first dose of the study drug, Study Day is calculated as Visit Date minus the first dose date. For visits after the first dose, Study Day is calculated as Visit Date minus the first dose date plus 1.
Screened	Subject who has signed informed consent.
Enrolled	Subject who has entered the RAAS dose titration/run-in period
Treated	Subject who has received a dose of the study drug.
Treatment Period	From the first dose to the last dose, inclusive, of the study drug
Follow-up Period	After the last dose, exclusive, of the study drug
Completer for the treatment	Subject who has completed the 12 weeks of the treatment period with Day 85 assessment.
Completer for the study	Subject who has completed the 12 weeks of the treatment period and follow-up period.
Baseline	Generally, baseline is defined as the non-missing value collected most recent to and before the time of the very first dose of the study drug unless specified otherwise. For urinary PCR, baseline will be the geometric mean of the two measurements made in the Day -7 to -2 window plus the Day 1 (pre-dose) value. For the eGFR, urinary ACR, MCP-1:creatinine ratio, EGF:MCP-1 ratio, and microscopic RBC count, baseline will be the geometric mean of the one measurement made in the Day -7 to 2 window plus the Day 1 (pre-dose) value.
Pre-treatment Adverse Event	Adverse event starting/worsening prior to the time of the first dose of the study drug administration.
Treatment Emergent Adverse Event	Adverse event starting/worsening between the first and last dose of the study drug administration.
Post-treatment Adverse Event	Adverse event starting/worsening after the last dose of the study drug.
Prior Medication	Medication on the Prior/Concomitant Medication CRF with start date prior to Study Day 1.
Concomitant Medication	Medication collected on the Prior/Concomitant Medication CRF with end date on/after Study Day 1, including missing end date or medication ongoing.

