10.2.11. Visit Windows

No visit window will be used. All data will be summarized by the evaluation visit recorded on the eCRF. In data listings, all dates will be presented along with the study day relative to the day of the first dose of the study drug.

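### As SAP 10.7.1 is written, the primary 12-week PCR slope includes values taken after CCX168 is stopped and rescue immunosuppression is started

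*SAP*

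**What the plan says.** **The slope rule.** The time-point table in SAP 10.7.1 lists the PCR values for Weeks 1 to 12 as "Day 1, Day 8, Day 15, Day 29, Day 57, and Day 85", with time values 0, 7, 14, 28, 56 and 85. The run-in slope is compared with the initial 4-week slope "as well as the full 12-week treatment period to evaluate the treatment effect of CCX168". No exception is made for subjects who have stopped the drug or been rescued.

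**What happens to such subjects.** Protocol 4.4: "In the event of treatment failure where rescue treatment such as corticosteroid therapy is needed, the study drug (CCX168) will be discontinued". It continues: "However, the subject will be asked to remain in the study and complete all remaining study visits". Subjects with confirmed worsening of eGFR or proteinuria "will exit the treatment phase of the study and be treated at the discretion of their primary nephrologist", and they too stay for follow-up and outcome recording.

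**The definition that points the other way.** SAP Section 6, Table 1, defines the Treatment Period as "From the first dose to the last dose, inclusive, of the study drug".

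**Other data rules.** SAP 10.2.9 keeps withdrawn subjects in the tables where applicable. SAP 10.2.10 says only that nothing is imputed. Under SAP 10.2.11, "All data will be summarized by the evaluation visit recorded on the eCRF". The mITT population (SAP Section 8) needs one dose and one post-baseline PCR, so rescued subjects belong to it.

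**The concern.** The protocol foresees PCR measurements under rescue immunosuppression and off CCX168. The SAP's visit list puts them into the slope that is meant to measure CCX168. Corticosteroids and similar agents are given to bring proteinuria down, so the subjects in whom CCX168 has failed may contribute late values that look like benefit. The trial is single-arm, so no control group would show the same effect of rescue. With up to about 20 subjects, each one carries about 1/20 = 5% of the mean slope.

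The SAP also disagrees with itself. Under Table 1, a slope over the treatment period would stop at the last dose. Under 10.7.1 it runs to Day 85. Two programmers working from the same SAP could produce different primary results.

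**Working it through.** The plan gives no figure for rescue or its effect, so there is none to reproduce. The check asks how far post-rescue values can move one subject's slope under the SAP's own time points.

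**Inputs.** Times 0, 7, 14, 28, 56, 85 (SAP 10.7.1). The footnote there subtracts one day, which would give 84 for Day 85. The tabled 85 is used, and the difference is trivial. All PCR values are assumed. On drug: 2.0, 2.6, 3.6, 5.4 g/g at Days 1, 8, 15, 29. The rise of 5.4 - 2.0 = 3.4 g/g exceeds the 3 g/g exit threshold in Protocol 4.4, subject to the repeat after 2 weeks. Rescue is assumed to start before Day 57.

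**Formula.** Least-squares slope = Σ(t - t̄)y / Σ(t - t̄)².

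**On-drug values only (to Day 29).** t̄ = 12.25 and Σ(t - t̄)² = 428.75. The numerator is -24.50 - 13.65 + 6.30 + 85.05 = 53.20. The slope is 53.20 / 428.75 = 0.124 g/g/day, or +124 mg/g/day.

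**All six visits.** t̄ = 190/6 = 31.67 and Σ(t - t̄)² = 5373.3. The first four visits contribute -63.33 - 64.13 - 63.60 - 19.80 = -210.87. Day 57 has deviation 24.33 and Day 85 has 53.33, so

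slope = (-210.87 + 24.33 × Day 57 + 53.33 × Day 85) / 5373.3.

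Day 85 alone holds 53.33² / 5373.3 = 53% of the squared time deviations.

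| Day 57 / Day 85 (g/g) | Numerator | Slope (mg/g/day) | Share of a mean over 20 |
|---|---|---|---|
| 3.0 / 1.2 | -73.9 | -13.7 | -0.7 |
| 4.0 / 2.0 | -6.9 | -1.3 | -0.1 |
| 4.0 / 2.5 | +19.8 | +3.7 | +0.2 |
| 4.0 / 3.0 | +46.5 | +8.6 | +0.4 |
| 5.4 / 3.0 | +80.5 | +15.0 | +0.7 |
| 5.4 / 4.0 | +133.9 | +24.9 | +1.2 |
| 5.4 / 5.4 (no fall) | +208.5 | +38.8 | +1.9 |

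The on-drug slope of +124 would contribute 124/20 = +6.2 to the same mean. The last row shows that part of the drop from +124 comes from the longer window and not from rescue. Within the same window, the post-rescue fall takes the slope from +39 to somewhere between +25 and -14.

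**When the sign reverses.** Setting the numerator to zero gives Day 85 = (210.87 - 24.33 × Day 57) / 53.33. The break-even Day 85 value is 2.6 g/g if Day 57 is 3.0, 2.1 if it is 4.0, and 1.5 if it is 5.4.

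**Stopping without rescue.** Assume a subject who improves on drug (2.0, 1.8, 1.6, 1.3), stops for another reason and rebounds to 2.0 and 2.2. On drug: (-24.50 - 9.45 + 2.80 + 20.475) / 428.75 = -24.9 mg/g/day. All visits: (-63.33 - 44.40 - 28.27 - 4.77 + 48.67 + 117.33) / 5373.3 = +4.7 mg/g/day. Here the all-visits rule works against CCX168.

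**The case against.** **Safeguards exist.** The per-protocol population (SAP Section 8) leaves out users of prohibited medication, which under Protocol 5.9 includes glucocorticoids, and the primary slope has its own per-protocol table (14.2.1.2). Protocol 7.12 allows sensitivity analyses that exclude visits with significant deviations. The Weeks 1 to 4 slope is planned as well, and in the example it is exactly the +124. It is less exposed because confirmed worsening needs a repeat after 2 weeks. These points stand, but only in part. The per-protocol analysis drops the failures altogether instead of counting them. Protocol 7.12 applies only if warranted and does not say whether rescue is a deviation. The stated primary endpoint is the 12-week slope.

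**Table 1 may already cut the values off.** That reading is possible, but the specific visit list in 10.7.1 does not use it. The ambiguity is itself a reason to fix the text.

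**Stronger readings a reader might infer.** One is that the primary mITT result is biased in favour of CCX168. The documents do not support that as a statement about the result: bias arises only if subjects are rescued or stop early, no rate is given, and stopping without rescue can push the other way. Protocol 7.2.4 names low cell counts and raised liver tests as other reasons for stopping. A second reading is that the slope rule contradicts the responder rule in SAP 10.7.2 and 10.7.3, which counts subjects who discontinued before Week 12 as non-responders. Those sections do not say whether drug or study is meant, so a conflict is not shown.

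**Truncation has a price.** Ending every stopper's slope at the last dose puts short, steep slopes into an unweighted paired t-test (+6.2 against -0.7 in a mean of 20). That stands, and it is why excluding values after rescue is easier to defend than truncating for every stopper.

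**Conclusion.** The point holds for rescued subjects. The visit list in SAP 10.7.1, taken with Protocol 4.4, attributes PCR values under rescue immunosuppression to CCX168, and it is not reconciled with Table 1. For one subject with the assumed on-drug worsening (+124 mg/g/day to Day 29), the all-visits slope lies between -14 and +25 mg/g/day over the post-rescue values examined. Attenuation follows from any fall after rescue; reversal of sign needs a large one. These figures rest on assumed PCR values and on rescue before Day 57. The effect on the group mean cannot be sized from the documents, and its net direction is open once stops without rescue are counted.

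**What to change.** In SAP 10.7.1:

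- State that the primary treatment-period slope uses no PCR value obtained after rescue immunosuppression starts.
- State how values after the last CCX168 dose without rescue are handled, and reconcile this with the Treatment Period in Table 1.
- Report the number of subjects affected by each rule.
- Present the slope with all visits and with on-drug values only, as sensitivity analyses.

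The cost is SAP wording and the extra sensitivity runs. Visits and data collection do not change. The drawback is that affected subjects' slopes rest on fewer points over a shorter window, so they are noisier and can be influential in the unweighted paired t-test. Showing the slope both ways lets the reader see how much depends on them.
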